10.3.2 Recording and Follow-up of Adverse Events and Serious Adverse Events

AE and SAE Recording

- When an AE/SAE occurs, it is the responsibility of the investigator to review all documentation (eg, hospital progress notes, laboratory reports, and diagnostics reports) related to the event.
- The investigator will then record all relevant AE/SAE information in the eCRF.
- It is **not** acceptable for the investigator to send photocopies of the patient's medical records/discharge summary to the CRO in lieu of completion of the AE/SAE CRF page.
- There may be instances when copies of medical records for certain cases are requested by the CRO. In this case, all patient identifiers, with the exception of the patient number, will be redacted on the copies of the medical records before submission to the CRO.
- The investigator will attempt to establish a diagnosis of the event based on signs, symptoms, and/or other clinical information. Whenever possible, the diagnosis (not the individual signs/symptoms) will be documented as the AE/SAE.

Assessment of Intensity

The investigator will make an assessment of intensity for each AE and SAE reported during the study and assign it to 1 of the following Common Terminology Criteria for Adverse Events (CTCAE) Version 5.0 grades

(https://ctep.cancer.gov/protocolDevelopment/electronic_applications/ctc.htm#ctc_50):

- Grade 1 Mild; asymptomatic or mild symptoms; clinical or diagnostic observations only; intervention not indicated.
- Grade 2 Moderate; minimal, local or noninvasive intervention indicated; limiting age-appropriate instrumental activities of daily living (ADL)*.
- Grade 3 Severe or medically significant but not immediately life-threatening; hospitalization or prolongation of hospitalization indicated; disabling; limiting self care ADL**.
- Grade 4 Life-threatening consequences; urgent intervention indicated.
- Grade 5 Death related to AE.
 - * Instrumental ADL refer to preparing meals, shopping for groceries or clothes, using the telephone, managing money, etc.
 - ** Self care ADL refer to bathing, dressing and undressing, feeding self, using the toilet, taking medications, and not bedridden.
- An event is defined as serious when it meets at least 1 of the predefined outcomes as described in the definition of an SAE, NOT when it is rated as Grades 3, 4, or 5.
- The highest severity during the period in which the AE occurred will be recorded in the eCRF.

Assessment of Causality

- The investigator is obligated to assess the relationship between study treatment and each occurrence of each AE/SAE.
- The relationship of an event to the study treatment will be determined by the investigator or subinvestigator according to the following criteria:
 - Related: An AE that can be reasonably explained as having been caused by the study treatment. For example, the occurrence of the AE can be explained by any of the following: a pharmacological effect of the study treatment (eg, a similar event had been reported previously); an increase/decrease of the dose affects the occurrence or seriousness of the AE; or all other causative factors (eg, medical history, concomitant medication, etc) have been ruled out after careful analysis of sufficient information.

- Not related: An AE that cannot be reasonably explained as having been caused by the study treatment.
- The investigator will use clinical judgment to determine the relationship.
- Alternative causes, such as underlying disease(s), concomitant therapy, and other risk factors, as well as the temporal relationship of the event to study treatment administration will be considered and investigated.
- The investigator will also consult the Investigator's Brochure and/or Product Information, for marketed products, in his/her assessment.
- The investigator should provide a rationale for the causality assessment in the Medical Comment field on the eCRF or if reporting via paper, the rationale for causality should be provided in the narrative section of the paper SAE form.
- There may be situations in which an SAE has occurred and the investigator has minimal information to include in the initial report to the CRO. However, **it is very important that the investigator always make an assessment of causality for every event before the initial transmission of the SAE data to the CRO.**
- The investigator may change his/her opinion of causality in light of follow-up information and send an SAE follow-up report with the updated causality assessment and update the eCRF.

Follow-up of AEs and SAEs

- The investigator is obligated to perform or arrange for the conduct of supplemental measurements and/or evaluations as medically indicated or as requested by the CRO to elucidate the nature and/or causality of the AE or SAE as fully as possible. This may include additional laboratory tests or investigations, histopathological examinations, or consultation with other health care professionals.
- If a patient dies during participation in the study or during a recognized follow-up period, the investigator will provide the CRO with a copy of any postmortem findings, including histopathology.
- New or updated information will be recorded in the eCRF.
- The investigator will submit any updated SAE data to the CRO within 24 hours of receipt of the information.

10.3.3 Reporting of Serious Adverse Events

All SAEs must be reported to the CRO in detail via EDC within 24 hours from the time point when the investigator or qualified designee first becomes aware of the SAE. If EDC is not available, complete the paper SAE case report form (CRF) and fax or e-mail it to:

Fax: [REDACTED]

E-mail: [REDACTED]

SAE Reporting to Shionogi via EDC

- The primary mechanism for reporting an SAE to the CRO will be EDC.
- If EDC is unavailable, then the site will use the paper SAE data collection (see next section).
- The site will enter the SAE data into EDC as soon as it becomes available.
- After the study is completed at a given site, EDC will be taken off-line to prevent the entry of new data or changes to existing data.

- If a site receives a report of a new SAE from a study patient or receives updated data on a previously reported SAE after EDC has been taken off-line, then the site should report this information on a paper SAE form (see next section) to the CRO or to the CRO's medical monitor by telephone/fax.

SAE Reporting to Shionogi via Paper CRF (if EDC is unavailable)

- Facsimile transmission of the SAE paper CRF is the preferred method to transmit this information to the CRO's medical monitor.
- In rare circumstances and in the absence of facsimile equipment, notification by telephone is acceptable with a copy of the SAE paper form sent by overnight mail or courier service.
- Initial notification via telephone does not replace the need for the investigator to complete and sign the SAE CRF pages within the designated reporting time frames.

10.4 Appendix 4: Contraceptive Guidance and Collection of Pregnancy Information

Definitions:

Woman of Childbearing Potential (WOCBP)

A female patient is considered a WOCBP following menarche if she meets 1 of the following criteria:

1. Not surgically sterile by hysterectomy, bilateral oophorectomy, and/or bilateral salpingectomy or tubal ligation with appropriate documentation of such surgery.
Note: Documentation can come from the site personnel's review of the patient's medical records, medical examination, or medical history interview.

OR

2. Not postmenopausal (defined as at least 12 months of spontaneous amenorrhea in a woman > 45 years of age)

Contraception Guidance:

Male patients

There are no specific requirements for contraceptive measures for male patients.

Female patients

Female patients of childbearing potential are eligible to participate if they are not pregnant (negative urine pregnancy test at Screening for WOCBP; see also below), not breastfeeding, and at least 1 of the following conditions applies:

- i. Postmenopausal (defined as at least 12 months of spontaneous amenorrhea in a woman > 45 years)
- ii. Surgically sterile by hysterectomy, bilateral oophorectomy, and/or bilateral salpingectomy or tubal ligation

- iii. Agree to use an acceptable effective form of birth control (with failure rates > 1% per year) from the start of Screening through 14 days after the last dose of study treatment, such as:
 - a. Progestogen-only oral hormonal contraception (where inhibition of ovulation is not the primary mode of action)
 - b. Male or female condom with or without spermicide
 - c. Cap, diaphragm, or sponge with spermicide

Pregnancy Testing:

- WOCBP should only be eligible after a verbally confirmed menstrual period and a negative urine pregnancy test.
- Pregnancy testing will be performed whenever a menstrual cycle is missed or when pregnancy is otherwise suspected.

Collection of Pregnancy Information:

Details of this procedure are described in [Section 8.3.5](#).

Male patients with partners who become pregnant

- The investigator or qualified designee will attempt to collect pregnancy information on any male patient's female partner who becomes pregnant while the male patient is in this study. This applies only to male patients who receive naldemedine.
- After obtaining the necessary signed informed consent from the pregnant female partner directly, the investigator or qualified designee will record pregnancy information on the paper Pregnancy Form and submit it to the CRO within 24 hours of learning of the partner's pregnancy. The female partner will also be followed to determine the outcome of the pregnancy. Information on the status of the mother and child will be forwarded to the CRO. Generally, follow-up will be no longer than 6 to 8 weeks following the estimated delivery date. Any termination of the pregnancy will be reported regardless of fetal status (presence or absence of anomalies) or indication for the procedure.

Female patients who become pregnant

- The investigator or qualified designee will collect pregnancy information on any female patient who becomes pregnant while participating in this study. Information will be recorded on the appropriate form and submitted to the CRO within 24 hours of learning of a patient's pregnancy. The patient will be followed to determine the outcome of the pregnancy. The investigator or qualified designee will collect follow-up information on the patient and the child and the information will be forwarded to the CRO. Generally, follow-up will not be required for longer than 6 to 8 weeks beyond the estimated delivery date. Any termination of pregnancy will be reported, regardless of fetal status (presence or absence of anomalies) or indication for the procedure.

- While pregnancy itself is not considered to be an AE or SAE, any pregnancy complication or termination of a pregnancy will be reported as an AE or SAE on the Pregnancy form. A spontaneous abortion is always considered to be an SAE and will be reported as such. Any poststudy pregnancy-related SAE considered reasonably related to the study treatment by the investigator or qualified designee will be reported to the CRO as described in [Section 8.3.4](#). While the investigator or qualified designee is not obligated to actively seek this information in former study patients, he or she may learn of an SAE through spontaneous reporting.
- Any female patient who becomes pregnant while participating in the study will discontinue study treatment and will be followed as described in this appendix (see also [Section 7.2](#) and [Section 8.3.5](#)).

All pregnancies must be reported to the CRO within 24 hours of becoming aware of the pregnancy. Complete the Pregnancy paper Form and fax or e-mail it to:

10.5 Appendix 5: Liver Safety: Suggested Actions and Follow-up Assessments

Liver Chemistry Stopping Criteria – Liver Stopping Event	
Alanine aminotransferase (ALT) or aspartate aminotransferase (AST) - absolute	ALT or AST $> 8 \times$ upper limit of normal (ULN) ¹ See additional actions and follow-up assessments listed below.
Increased bilirubin and international normalized ratio (INR)	ALT or AST $> 3 \times$ ULN AND total bilirubin $> 2 \times$ ULN or INR > 1.5 ; also report as a serious adverse event (SAE). ²
Symptomatic	ALT or AST $> 3 \times$ ULN accompanied by fatigue, nausea, vomiting, right upper quadrant pain or tenderness, fever, rash, and/or eosinophilia ($> 5\%$); also, report as an SAE.
Suggested Actions and Follow-up Assessments	
Actions	

• Immediately discontinue study intervention.• Report the event to the contract research organization (CRO) within 24 hours• Complete the liver event electronic case report form (eCRF), and complete an SAE data collection tool if the event also met the criteria for an SAE.²• Perform liver chemistry follow-up assessments.• Monitor the patient until liver chemistry test abnormalities resolve, stabilize, or return to baseline (see MONITORING).• Do not restart/rechallenge patient with study intervention unless allowed per protocol and CRO approval is granted.• If restart/rechallenge is either not allowed per protocol or not granted, permanently discontinue study intervention. The patient may continue in the study for any protocol-specified follow-up assessments	
Follow-up Assessments	

• Viral hepatitis serology³• Obtain INR and recheck with each liver chemistry assessment until the transaminases values show downward trend• Obtain blood sample for pharmacokinetic (PK) analysis immediately after the event occurs⁴• Serum creatine phosphokinase (CPK) and lactate dehydrogenase (LDH)• Fractionate bilirubin, if total bilirubin $\geq 2 \times$ ULN• Obtain complete blood count with differential to assess eosinophilia• Record the appearance or worsening of clinical symptoms of liver injury, or hypersensitivity, on the adverse event (AE) eCRF	


MONITORING:
 
If ALT or AST > 3 × ULN AND total bilirubin > 2 × ULN or INR > 1.5:
 
Repeat liver chemistry tests (include ALT, aspartate transaminase [AST], alkaline phosphatase [ALP], bilirubin, and INR) and perform liver event follow-up assessments within 24 hours.Monitor patient twice weekly until liver chemistry test abnormalities resolve, stabilize, or return to baseline.A specialist or hepatology consultation is recommended. 
If ALT or AST > 3 × ULN AND total bilirubin < 2 × ULN or INR ≤ 1.5:
 
Repeat liver chemistry tests (include ALT, AST, ALP, bilirubin, and INR) and perform liver chemistry follow-up assessments within 24 to 72 hours.Monitor patients weekly until liver chemistry abnormalities resolve, stabilize, or return to baseline.	
Record use of concomitant medications (including acetaminophen, herbal remedies, and other over-the-counter medications) on the concomitant medications eCRF.Record alcohol use on the liver event alcohol intake eCRF. 
If ALT or AST > 3 × ULN AND total bilirubin > 2 × ULN or INR > 1.5:
 
Anti-nuclear antibody, anti-smooth muscle antibody, Type 1 anti-liver kidney microsomal antibodies, and quantitative total immunoglobulin G (IgG) or gamma globulins.Serum acetaminophen adduct high performance liquid chromatography (HPLC) assay (quantifies potential acetaminophen contribution to liver injury in patients with definite or likely acetaminophen use in the preceding week [5]).Liver imaging (ultrasound, magnetic resonance, or computerized tomography) and/or liver biopsy to evaluate liver disease; complete liver imaging and/or liver biopsy in eCRFs.
---	--

1. All events of ALT or AST $> 3 \times$ ULN **AND** total bilirubin $> 2 \times$ ULN or INR > 1.5 may indicate severe liver injury **and must be reported as an SAE (excluding studies of hepatic impairment or cirrhosis)**. The INR stated threshold value will not apply to patients receiving anticoagulants.
2. Serum bilirubin fractionation should be performed if testing is available. If serum bilirubin fractionation is not immediately available, discontinue study intervention if ALT or AST $> 3 \times$ ULN **and** total bilirubin $> 2 \times$ ULN. Additionally, if serum bilirubin fractionation testing is unavailable, **record the absence/presence of detectable urinary bilirubin on dipstick** which is indicative of direct bilirubin elevations suggesting liver injury.
3. hepatitis A immunoglobulin M (IgM) antibody; hepatitis B surface antigen (HBsAg) and hepatitis B core antibody (HBcAb); hepatitis C RNA; cytomegalovirus IgM antibody; Epstein-Barr viral capsid antigen IgM antibody (or if unavailable, heterophile antibody or monospot testing); and hepatitis E IgM antibody.
4. Pharmacokinetic sample may not be required for patients known to be receiving placebo or noncomparator interventions. Record the date/time of the PK blood sample draw and the date/time of the last dose of study intervention prior to the PK blood sample draw on the CRF. If the date or time of the last dose is unclear, provide the patient's best approximation. If the date/time of the last dose cannot be approximated OR a PK sample cannot be collected in the time period indicated above, do not obtain a PK sample. Instructions for sample handling and shipping are in the PK laboratory manual.

ALT = alanine transaminase; INR = international normalized ratio; SAE = serious adverse event;
ULN = upper limit of normal

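### The lighter row of the liver monitoring table is not the complement of the stricter row, so a patient off anticoagulants with only bilirubin or only INR raised meets both schedules

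*Protocol*

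**What the plan says.** Protocol Section 10.5 (Appendix 5), under MONITORING, splits patients with raised transaminases into two rows.

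- **Row 1** (stricter): "If ALT or AST > 3 × ULN AND total bilirubin > 2 × ULN or INR > 1.5". The site is to repeat the liver tests and "perform liver event follow-up assessments within 24 hours", then "Monitor patient twice weekly until liver chemistry test abnormalities resolve, stabilize, or return to baseline". It adds: "A specialist or hepatology consultation is recommended".
- **Row 2** (lighter): "If ALT or AST > 3 × ULN AND total bilirubin < 2 × ULN or INR ≤ 1.5". The site is to repeat the tests and "perform liver chemistry follow-up assessments within 24 to 72 hours", then "Monitor patients weekly until liver chemistry abnormalities resolve, stabilize, or return to baseline". It gives no consultation advice.

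Footnote 1 of the same appendix states: "The INR stated threshold value will not apply to patients receiving anticoagulants".

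The stopping criteria at the head of the appendix use the row 1 condition to define a liver stopping event that is also an SAE, and the list of actions then sends the site to MONITORING for follow-up. Footnote 1 says that this condition may indicate severe liver injury. No visible text says which row governs if both apply.

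**The concern.** Two rows that set different schedules should divide the patients between them. Row 1 is met when either bilirubin or INR is raised, so row 2 should be met only when neither is. Row 2 instead joins its two clauses with *or*, so one normal value is enough to enter it, even when the other value has already put the patient in row 1.

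The overlap falls on a pattern that the protocol itself classes as a stopping event and possible severe liver injury. At stake are the time to the first repeat test, the frequency of monitoring and whether a specialist is consulted. Nothing else in the liver procedures depends on row 2.

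**Working it through.** No sample size, power or error rate is involved. The check is a truth table.

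**Inputs** (Protocol Section 10.5, MONITORING and footnote 1). Let A = ALT or AST > 3 × ULN, TB = total bilirubin in multiples of ULN.

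- Row 1: A and (TB > 2 or INR > 1.5)
- Row 2: A and (TB < 2 or INR ≤ 1.5)
- On anticoagulants the INR clause is dropped from both rows.

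**What row 2 should be.** By De Morgan's rule, the complement of (TB > 2 or INR > 1.5) is (TB ≤ 2 and INR ≤ 1.5). Row 2 differs in two ways: *or* in place of *and*, and < in place of ≤ for bilirubin.

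**Enumeration, with A true throughout**

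| Anticoagulants | TB (× ULN) | INR | Row 1 | Row 2 as written | Result | Row 2 corrected | Result |
|---|---|---|---|---|---|---|---|
| No | < 2 | ≤ 1.5 | no | yes | row 2 | yes | row 2 |
| No | < 2 | > 1.5 | yes | yes | **both** | no | row 1 |
| No | = 2 | ≤ 1.5 | no | yes | row 2 | yes | row 2 |
| No | = 2 | > 1.5 | yes | no | row 1 | no | row 1 |
| No | > 2 | ≤ 1.5 | yes | yes | **both** | no | row 1 |
| No | > 2 | > 1.5 | yes | no | row 1 | no | row 1 |
| Yes | < 2 | not applied | no | yes | row 2 | yes | row 2 |
| Yes | = 2 | not applied | no | no | **neither** | yes | row 2 |
| Yes | > 2 | not applied | yes | no | row 1 | no | row 1 |

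**Counts as written.** Off anticoagulants: 2 of 6 in both rows, 0 of 6 in neither. On anticoagulants: 0 of 3 in both, 1 of 3 in neither. In all, 9 − 2 − 1 = 6 of 9 patterns fall in exactly one row. With the corrected row 2, 9 of 9 do.

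**Worked cases, off anticoagulants.** TB 3 × ULN with INR 1.0 meets row 1 through bilirubin and row 2 through INR. TB 1 × ULN with INR 2.0 meets row 1 through INR and row 2 through bilirubin.

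**Sensitivity to grouping.** Reading each condition as (A and bilirubin clause) or INR clause, instead of A and (bilirubin clause or INR clause), gives the same overlap when A holds.

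**Difference between the schedules for an overlapping patient.** Latest first repeat: 72 − 24 = 48 hours later under row 2. Monitoring: once against twice a week, a ratio of 1/2. Consultation: recommended in row 1, not mentioned in row 2.

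**Is the wording genuine?** Yes. The Version 2 entry for Section 10.5 in Protocol Section 10.10 (Appendix 10) gives the same row 2 condition, so it is not an error of text extraction.

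**The case against.** The strongest reply is that the rows overlap without conflicting. Row 1 applies to every patient with either value raised, and nothing in row 2 releases the site from it. A repeat at 24 hours fits both windows, and twice-weekly monitoring also covers weekly. A site that followed only row 2 would breach row 1. Intent is also clear elsewhere: the stopping criteria, the heading of the extended work-up, footnote 1 and the laboratory footnote in Section 10.2 (Appendix 2) all put a single raised value in the severe class. Such a patient already stops study drug, is reported to the CRO within 24 hours and counts as an SAE. No endpoint uses these rows; SAP Table 5 has its own combined liver criterion.

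All of that stands, and it keeps the practical impact low. It means that the 48 hours and the halved frequency arise only if a site takes row 2 alone. It does not make row 2 correct: a site that finds its patient described in row 2 has to infer from other text that row 2 was not meant.

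The version history also records a flowchart added to Section 10.5, which could not be seen for this review. It may show which row takes precedence, but the wording of row 2 would still be wrong.

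Two objections concern the correction. First, an anticoagulated patient with normal bilirubin and an INR of, say, 2.5 meets the corrected row 2 only if footnote 1 is read as removing the INR clause. That is the natural reading of the footnote, and the table above assumes it. Second, the correction puts bilirubin exactly 2 × ULN in the lighter row when INR is ≤ 1.5 or not applied, whereas bilirubin fractionation and SAP Table 5 use ≥ 2 × ULN. The placement follows the protocol's own stopping trigger, which is strictly above 2 × ULN, and SAP Table 5 is a summary criterion that does not direct sites.

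**Conclusion.** The concern holds. As written, row 2 is not the complement of row 1. Off anticoagulants, 2 of 6 patterns meet both schedules; on anticoagulants, 1 of 3 meets neither, and that gap (bilirubin exactly 2 × ULN) is trivial. The ambiguity is limited to the retest window, the monitoring frequency and the consultation advice. Stopping, SAE reporting and the extended work-up follow the row 1 condition and are not affected.

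These are counts of logical patterns, not of patients. The documents give no expected frequency of ALT or AST above 3 × ULN, so the number of patients affected cannot be estimated. The result assumes that footnote 1 removes the INR clause from both rows for anticoagulated patients. It is a drafting error in an operative safety instruction: low in impact, but one that should be corrected.

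**What to change.** Change row 2 only, so that its condition reads: *ALT or AST > 3 × ULN AND total bilirubin ≤ 2 × ULN and INR ≤ 1.5*. Every patient off anticoagulants with either value raised then falls in row 1 alone, and bilirubin exactly 2 × ULN has a row in every case. A pointer from row 2 to footnote 1 would remove any doubt about anticoagulated patients, but is optional. If the Section 10.5 flowchart repeats the row 2 condition, give it the same wording. Row 1, the stopping criteria and the Section 10.2 laboratory footnote need no *and*/*or* change.

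The cost is one line of text, with no new procedure, data item or analysis. As a protocol change it needs the authority or IRB approval described in Section 10.1.1, as applicable.
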